8.2.6. Analgesic Use

From Day1 through the follow-up visit (EOS), participants will complete a daily electronic diary of their analgesic use (yes/no; refer to the Study Manual). All analgesics and dose modifications will be captured in the source and on the appropriate eCRF.

8.2.7. Hidradenitis Suppurativa Patient Global Impression of Change

Participants will complete the HS-PGIC questionnaire at the designated study visits listed in [Table 3](#). The HS-PGIC consists of 1 self-administered item that assesses change in the severity of skin in the HS area. Participants are asked to indicate their impression of change compared with their previous visit. The participant will answer the following: "Since your last visit, your HS is: (1) very much improved, (2) much improved, (3) minimally improved, (4) no change, (5) minimally worse, (6) much worse, or (7) very much worse." The participant should complete the questionnaire before site personnel perform any efficacy assessments.

8.2.8. Dermatology Life Quality Index

Participants will complete a DLQI questionnaire (refer to the Study Manual) from Day1 through the follow-up visit (EOS). The DLQI will be used to assess the symptoms and the impact of skin problems on quality of life ([Hongbo et al 2005](#)). The DLQI can be used to evaluate the impact of HS on daily activities, based on 6 areas: symptoms and feelings, daily activities, leisure, work and school, personal relationships, and treatment. Participants will be asked to respond to the 10 items of the DLQI based on a recall period of "the last week." Decreased scores indicate improved health-related quality of life. The participant should complete the questionnaire before site personnel perform any efficacy assessments.

8.2.9. Photography of Target Lesions

For participants who consent to photography, a target area for each participant will be identified at screening and the same area should be photographed at visits specified in [Table 3](#) for purposes of documentation. The lesion should be located in an area with inflammatory nodules and/or abscesses that are a good representation of the disease severity.

8.3. Safety Assessments

8.3.1. Adverse Events

Adverse events will be monitored from the time the participant signs the ICF up until the end of the safety follow-up period. Adverse events that begin or worsen after informed consent should be recorded on the Adverse Event Form in the eCRF regardless of the assumption of a causal relationship with the study drug. Conditions that were already present at the time of informed consent should be recorded on the Medical History Form in the eCRF. Adverse events (including laboratory abnormalities that constitute AEs) should be described using a diagnosis whenever possible rather than by individual underlying signs and symptoms.

Adverse events will be reported by the participant (or, when appropriate, by a caregiver, surrogate, or the participant's legally authorized representative). The investigator and any qualified designees are responsible for detecting, documenting, and recording events that meet the definition of an AE or SAE and remain responsible for following-up on AEs that are serious,

considered related to the study treatment, or that caused the participant to discontinue the study treatment. Care will be taken not to introduce bias when detecting AEs and/or SAEs. Open-ended and nonleading verbal questioning of the participant, such as "How are you feeling?" is the preferred method to inquire about AE occurrences. Adverse events may also be detected when they are volunteered by the participant during the screening process or between visits, or through physical examinations, laboratory tests, or other assessments. The definition, reporting, and recording requirements for AEs are described in Section 9.

All SAEs will be recorded and reported to the sponsor or designee within 24 hours. The investigator will submit any updated SAE data to the sponsor within 24 hours of it being available.

After the initial AE/SAE report, the investigator is required to proactively follow each participant at subsequent visits/contacts. All SAEs will be followed until resolution, stabilization, the event is otherwise explained, or the participant is lost to follow-up (as defined in Section 7.3).

8.3.2. Physical Examinations

Physical examinations will be conducted at the time points listed in [Table 3](#).

A comprehensive physical examination will include height and body weight and assessment of the following organ or body systems: skin; head, eyes, ears, nose, and throat; thyroid; lungs; cardiovascular system; abdomen (liver, spleen); extremities; and lymph nodes. A brief neurological examination will also be performed.

A targeted physical examination should be conducted as indicated by symptoms reported by the participant, AEs, or other findings. Abnormalities that are considered clinically significant in the judgment of the investigator are to be reported as AEs.

Physical examinations must be performed by a medically qualified individual such as a licensed physician, physician's assistant, or an advanced registered nurse practitioner, as local law permits.

8.3.3. Vital Signs

Vital sign measurements include blood pressure, pulse, respiratory rate, and body temperature. Blood pressure and pulse will be taken with the participant in the recumbent, semirecumbent, or sitting position after 5 minutes of rest. Any abnormalities that are considered clinically significant in the judgment of the investigator are to be reported as AEs.

8.3.4. Electrocardiograms

All 12-lead ECGs will be performed with the participant in a recumbent or semirecumbent position after at least 5 minutes of rest. Electrocardiograms should be performed as indicated in [Table 3](#) and [Table 10](#). Additional 12-lead ECGs may be performed at other visits as deemed clinically necessary.

Electrocardiograms will be interpreted by the investigator at the site or designee, and the results will be used for immediate management of the participant's care. The decision to include or exclude a participant or withdraw a participant from the study based on an ECG flagged as "Abnormal, Clinically Significant" is the responsibility of the investigator, in consultation with the sponsor's medical monitor, as appropriate. Any abnormalities that are considered clinically significant in the judgment of the investigator are to be reported as AEs.

Table 10: Electrocardiogram Schedule

Study Visit	Timing of Electrocardiogram Relative to Administration of Study Drug		
	Not Applicable	Predose (Trough) ECG ^a	Postdose (Postdose 2) ECG ^b
Screening ^c	Single → Triple ^d		
Day 1		Triple ^e	Single → Triple ^d
Week 4		Single → Triple ^d	Single → Triple ^d
Week 8		Single → Triple ^d	

^a Predose ECG should be performed 5 to 10 minutes before the predose [REDACTED].

^b Postdose ECGs will be performed after participants complete all of the study assessments but before the collection of the second postdose (postdose 2) [REDACTED] (see Table 12). Postdose ECG will be measured [REDACTED]

^c Prolonged QTcF values of ≥ 450 msec at screening are to be confirmed by performing 2 additional ECGs and averaging the results to determine whether the averaged value meets the exclusion criterion.

^d Single → Triple: Single ECG will be performed first. If prolonged QT interval (corrected for heart rate using Fridericia's formula [QTcF], defined as ≥ 450 msec) are observed, an additional 2 ECGs will be measured within the next 5 minutes.

^e Day 1 predose ECG will be performed in triplicate, and values will be averaged to calculate the baseline values.

8.3.5. Laboratory Assessments

8.3.5.1. Safety Assessments

Required laboratory tests are listed in Table 11. Safety laboratory tests include hematology, chemistry, CRP, and lipid panel (see Table 3). Participants may have a light snack before these visits but should allow for an overnight fast (at least 8 hours) before sample collection for the lipid panel.

If there is a potential clinically significant abnormality in hematology or chemistry assessments (particularly in platelet count) at Weeks 2, 4 or 6, then an unscheduled visit the following week (Weeks 3, 5, 7; see Section 8.6) to repeat laboratory assessments is required.

Clinical laboratory tests will be performed at a central laboratory (refer to the Laboratory Manual for sample handling and shipping instructions).

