1. PROTOCOL SUMMARY

Protocol Title: A Phase 2, Dose-Escalation, Placebo-Controlled Study of the Safety of INCB054707 in Participants With Hidradenitis Suppurativa

Protocol Number: INCB 54707-203

Objectives and Endpoints:

[Table 1](#) presents the primary and key secondary objectives and endpoints.

Table 1: Primary and Key Secondary Objectives and Endpoints

Objectives	Endpoints
Primary	
To determine the safety and tolerability of INCB054707.	
Frequency, duration, and severity of AEs, clinical laboratory test results, vital signs results, ECGs, and physical examination findings.
Key Secondary	
To determine the systemic exposure to INCB054707.	
Population PK parameters of INCB054707.
To determine the efficacy of INCB054707.	
Proportion of participants achieving a HiSCR at each visit.Proportion of participants achieving an AN count of 0 to 2 at each visit.Mean change from baseline in the HS Pain NRS scores, worst and average pain, at each visit.Mean change from baseline to Week 8 in the modified Sartorius scale score.Mean change from baseline in the number of draining fistulas count at each visit.Proportion of participants at each category of Hurley Stage at baseline and Week 8.Proportion of participants with change from baseline in Hurley Stage at Week 8.Proportions of participants in each HS-PGIC category during the treatment period.Actual measurements in HS-PGIC at each visit.

Overall Design:

[figure not shown]
[Table 2](#) presents the key study design elements. Further study details are presented after the table.

Table 2: Key Study Design Elements

Study Phase	Phase 2
Clinical Indication	HS
Population	Men and women aged 18 to 75 years with moderate to severe HS for at least 6 months
Number of Participants	The study includes 3 cohorts and approximately 36 participants will be enrolled. In each cohort, approximately 12 participants will be randomized 3:1 (INCB054707:placebo) to 1 of 2 treatment groups.
Study Design	Randomized, dose escalation, placebo-control
Estimated Duration of Study Participation	The study will consist of a screening period of up to 28 days, an 8-week treatment period, and a 30-day safety follow-up period. The estimated total duration of study participation is approximately 16 weeks for each participant.
Data Safety Monitoring Board	No

Treatment Groups and Duration:

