The study design is shown in [Figure 1](#) below. The schedule of assessments is detailed in [Table 3](#).

The study includes 3 cohorts and approximately 36 participants will be enrolled. In each cohort, approximately 12 participants will be randomized to receive either INCB054707 (n = 9) or placebo (n = 3). The total duration of therapy for all enrolled participants is 8 weeks with a 30-day safety follow-up period. Cohort progression will be determined by the SRC evaluation of safety data following completion of Week 4 of all participants from a cohort (see Section [6.5.2](#)).

Table 3: Schedule of Assessments

Evaluation	Section	Screening	Treatment						Safety Follow-Up
		Day -28 to -1	Day 1 ^a	Week 1 ± 1 day	Week 2 ^b ± 3 days	Week 4 ^a ± 3 days	Week 6 ^b ± 3 days	Week 8 ^a ± 3 days (EOT)	
Administrative/screening procedures									
Informed consent	8.1.1	X							
Demography/medical history	8.1.6	X							
Inclusion/exclusion criteria	5	X	X						
Prior/concomitant medications	6.7	X	X	X	X	X	X	X	X
Serology	8.3.5.2	X							
Urinalysis	8.3.5.2	X							X
TB screening	8.3.5.2	X							
FSH ^c	8.3.5.2	X							
Pregnancy testing ^d	8.3.5.3	X	X	X	X	X	X	X	X
Contact IWRS	8.1.3	X	X	X	X	X	X	X	
Randomization to treatment arm	8.1.3		X						
Dispense study drug	6.1		X			X			
Collect study drug and assess compliance	6.4			X	X	X	X	X	
Distribute reminder cards	8.1.4	X	X	X	X	X	X	X	
Electronic diary verification	8.1.5		X	X	X	X	X	X	X
Safety procedures/assessments									
Comprehensive physical examination ^e	8.3.2	X						X	
Targeted physical examination	8.3.2		X	X	X	X	X		X
Vital signs	8.3.3	X	X	X	X	X	X	X	X
Hematology and chemistry assessments ^f	8.3.5.1, 8.6	X	X	X	X ^f	X ^f	X ^f	X	X
Lipid panel	8.3.5.1		X						X
CRP	8.3.5.1		X						X
12-lead ECG (screening) ^g	8.3.4	X							
12-lead ECG (predose and postdose) ^g	8.3.4		X			X			
12-lead ECG (predose only) ^g	8.3.4							X	
Assess AEs	8.3.1, 9	X	X	X	X	X	X	X	X

Table 3: Schedule of Assessments (Continued)

Evaluation	Section	Screening	Treatment						Safety Follow-Up
		Day -28 to -1	Day 1 ^a	Week 1 ± 1 day	Week 2 ^b ± 3 days	Week 4 ^a ± 3 days	Week 6 ^b ± 3 days	Week 8 ^a ± 3 days (EOT)	
Efficacy assessments									
Hurley Stage	8.2.1	X						X	X
AN count (HiSCR)	8.2.2	X	X	X	X	X	X	X	X
Modified Sartorius score	8.2.3		X					X	X
Record rescue lesional treatment	8.2.4			X	X	X	X	X	X
HS Pain NRS ^c	8.2.5		X	X	X	X	X	X	X
Evaluate daily analgesic use	8.2.6		X	X	X	X	X	X	X
HS-PGIC	8.2.7			X	X	X	X	X	X
DLQI	8.2.8		X	X	X	X	X	X	X

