6.5.1. Definition of a Dose-Limiting Toxicity

Dose-limiting toxicity will be defined as the occurrence of any of the events listed in Table 7 occurring up to Week 8 (EOT), except those with a clear alternative explanation not related to study drug. All DLTs will be assessed for severity by the investigator using CTCAE v4.03 criteria. Participants who receive at least 1 dose of study drug at the level assigned or have a DLT will be considered evaluable for determining tolerability of the dose.

Table 7: Definition of Dose-Limiting Toxicity

Toxicity	Definition
Nonhematologic	
 Any liver function abnormalities that meet the definition of Hy's law.^a Any \geq Grade 3 nonhematologic toxicity EXCEPT: 
 Transient (\leq 72 hours) abnormal laboratory values without associated clinically significant signs or symptoms. Nausea, vomiting, and diarrhea adequately controlled with medical therapy within 48 hours. An event clearly associated with the underlying disease, disease progression, a concomitant medication, or comorbidity. Asymptomatic changes in lipid profiles.
Hematologic	
 Grade 2 neutropenia (neutrophils: 1 to $< 1.5 \times 10^9/L$) with \geq Grade 3 infection. \geq Grade 3 neutropenia (neutrophils: $< 1 \times 10^9/L$). \geq Grade 2 thrombocytopenia (platelets: $< 75 \times 10^9/L$). Grade 4 anemia (hemoglobin: $< 6.5 \text{ g/dL}$).
Events of special interest	
 Serious infections due to bacterial, mycobacterial, invasive fungal, viral, or other opportunistic pathogens; viral reactivation; malignancy.

^a Hy's law is defined as 1) ALT or AST elevation $> 3 \times \text{ULN}$, 2) total bilirubin $> 2 \times \text{ULN}$ without initial findings of cholestasis (elevated serum alkaline phosphatase), AND 3) no other apparent possible causes of aminotransferase elevation and hyperbilirubinemia, including, but not limited to, viral hepatitis, pre-existing chronic or acute liver disease, or the administration of other drug(s) known to be hepatotoxic.

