6.5.2. Procedures for Cohort Review and Dose Escalation

After all participants in each cohort have completed the Week 4 visit and assessments, a SRC will review safety data on a blinded basis from that cohort. If blinded data are determined to support the safety and tolerability of the dose for that cohort, the next higher dose cohort may open to enrollment. If necessary, the SRC may request to further review unblinded safety data from that cohort at Week 4. In the case that the unblinded data at Week 4 is not enough to support dose escalation, the SRC can also choose to wait until all participants complete Week 8 assessment and then make the decision. The SRC could also make a recommendation to expand a cohort to obtain additional safety data.

A participant's randomization will be unblinded for the SRC if the participant experiences any of the DLTs listed in [Table 7](#) and the DLT is attributed to study drug. If ≥ 3 participants in any cohort treated with INCB054707 have DLTs or the study drug is considered not tolerable, then the escalation will be terminated.

After the completion of a cohort, the sponsor may also be unblinded to safety and efficacy data from that cohort.

Telephone conferences will also be scheduled by the sponsor with active study investigators in order to review cohort-specific data and overall safety data, agree on dose escalation, adjudicate individual high-grade AEs as potentially dose-limiting, and guide other major study decisions.

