8.1.4. Distribution of Reminder Cards

Participants will be provided with a reminder card at the visits indicated at [Table 3](#). The reminder card will indicate the date/time of the next visit and will also remind the participant that they should not take study drug on Day 1, Week 4, and Week 8 as they will take it after blood draws for safety evaluation have been completed.

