8.8. Safety Follow-Up

The safety follow-up period is the interval between the EOT visit and the scheduled safety follow-up visit, which should occur 30 to 35 days after the EOT visit (or after the last dose of study drug if the EOT visit was not performed). Adverse events and SAEs must be reported up until the end of the safety follow-up period, the date of the follow-up visit, or until toxicities resolve, return to baseline, or are deemed irreversible, whichever is longer. Reasonable efforts should be made to have the participant return for the follow-up visit and report any AEs that may occur during this period.

For purposes of analysis, participants who complete through Week 8 will be considered to have completed the study.

9. ADVERSE EVENTS: DEFINITIONS AND PROCEDURES FOR RECORDING, EVALUATING, FOLLOW-UP, AND REPORTING

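### The visible schedule has no on-treatment lipid panel or CRP sample: both tests are marked only before the first dose and 30 to 35 days after end of treatment

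*Protocol*

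**What the plan says.** Protocol 8.3.5.1 defines the set and points to the schedule for timing: "Safety laboratory tests include hematology, chemistry, CRP, and lipid panel (see Table 3"). SAP 8.3.2 also names the lipid panel and CRP among the clinical laboratory tests. The primary endpoint (Protocol Table 1) covers "Frequency, duration, and severity of AEs, clinical laboratory test results, vital signs results, ECGs, and physical examination findings".

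In the visible Table 3, the lipid panel and CRP rows each carry two marks, at Day 1 and at Safety Follow-Up. The hematology and chemistry row is marked at every visit.

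Four other provisions fix what those two marks mean:

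- **Day 1 is predose.** Protocol 8.1.4 tells participants not to take study drug before the Day 1, Week 4 and Week 8 visits, as "they will take it after blood draws for safety evaluation have been completed".
- **Follow-up is off drug.** Protocol 8.8 places the follow-up visit in a window "which should occur 30 to 35 days after the EOT visit".
- **Lipid changes are foreseen.** Protocol 6.5.1 counts dose-limiting toxicities (DLTs) "occurring up to Week 8 (EOT"), and Table 7 lists among its exceptions "Asymptomatic changes in lipid profiles".
- **Review falls during treatment.** Under Protocol 6.5.2, once a cohort has completed Week 4, "a SRC will review safety data on a blinded basis from that cohort". The safety review committee (SRC) may also wait for Week 8 data.

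On analysis, SAP 8.3.1 summarizes laboratory values and changes from baseline by visit. SAP 8.3.2 restricts worst-postbaseline shift tables to values obtained no more than 30 days after treatment stops.

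**The concern.** A safety laboratory test is normally sampled while participants take the drug. Here, two tests that the protocol itself calls safety tests have one scheduled value before exposure and one about a month after it ends. If the drug shifts lipids or CRP and the shift reverses on stopping, the scheduled data could show little or nothing in any dose group. The placebo group does not help, because it follows the same schedule.

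At stake is the laboratory part of the primary safety summary. Protocol 2.2.1 also expects this study to inform a larger dose-ranging Phase 2b study. On the visible schedule, it would hand over no systematic on-treatment lipid or CRP data at any dose.

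**Working it through.** **1. The plan's own figure.** The only power-type figure is the chance of seeing at least one adverse event of interest with 9 participants at a 20% rate: 1 − 0.8^9 = 0.866, which agrees with the stated value above 85%. It is not an input here, and its examples name neither lipids nor CRP.

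**2. Reading Table 3.** Marks by visit:

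| Row | Screening | Day 1 | Wk 1 | Wk 2 | Wk 4 | Wk 6 | Wk 8 | Follow-Up |
|---|---|---|---|---|---|---|---|---|
| Lipid panel | – | X | – | – | – | – | – | X |
| CRP | – | X | – | – | – | – | – | X |
| Hematology and chemistry | X | X | X | X | X | X | X | X |
| Modified Sartorius (check) | – | X | – | – | – | – | X | X |
| Comprehensive physical examination (check) | X | – | – | – | – | – | X | – |

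The two check rows test whether text extraction has shifted a column. Modified Sartorius is marked at both Week 8 and Follow-Up, in line with its baseline-to-Week-8 endpoint. The comprehensive examination is marked at Week 8 but not at Follow-Up. The two columns are therefore distinct, and the second lipid and CRP mark belongs to Follow-Up.

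**3. Count.** On-treatment visits are Weeks 1, 2, 4, 6 and 8, which is 5. Lipid panel: 0 of 5. CRP: 0 of 5. Hematology and chemistry: 5 of 5. Each of the two tests has one scheduled postbaseline value, taken off drug. The SRC would have no scheduled on-treatment value of either test at Week 4, or at Week 8 if it waits.

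**4. What the SAP can do with the follow-up value.** By-visit summaries have no 30-day limit, so the value can appear there. For a shift table, compare the visit window with the limit:

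- Last dose on the EOT day: follow-up falls on days 30 to 35 after the last dose, so 1 of the 6 allowed days (day 30) qualifies.
- Last dose one day before EOT: days 31 to 36, so 0 of 6 qualify.

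This counts permitted days and does not forecast visit dates. Protocol 7.1.2, for example, describes follow-up after discontinuation as the discontinuation date plus 30 days.

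**5. Fasting marks.** Footnote a of Table 3 requires an overnight fast at Day 1, Week 4 and Week 8. Two of these visits have no visible lipid mark. The amendment summary (Appendix B, item 2) explains that Week 1 needs no fast because neither lipids nor biomarker serum is drawn there. The Week 4 and Week 8 fasts may therefore serve biomarker sampling that is not visible. They do not show that a lipid draw was intended.

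**6. Cost.** About 36 participants × 1 visit = 36 assays of each test; × 2 visits = 72.

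**The case against.** The strongest reply is that this is a deliberate, low-priority design choice. Table 7 exempts asymptomatic lipid changes, Table 8 has no lipid- or CRP-specific action, neither test is an adverse event of special interest, and Protocol 8.6 allows unscheduled tests. A baseline value and a follow-up check would fit that priority.

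Part of this stands: no visible decision rule depends on these values. It does not remove the point. Both tests are named safety tests within a primary endpoint, and tests ordered on clinical indication cannot systematically find a silent laboratory change.

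The second reply is that the visible table may not be the whole schedule. This stands as a limit. Table 11 and Sections 8.4 and 8.5 cannot be seen, and the fasts at Weeks 4 and 8 suggest some sampling there that is not shown.

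A reader might go further in four directions that the documents do not support:

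- **That no lipid or CRP data are collected on treatment.** Only the visible schedule can be judged.
- **That dose escalation is compromised.** Escalation turns on DLTs or tolerability, and asymptomatic lipid changes are exempt from the DLT definition.
- **That the lost signal can be sized.** The documents give no rate at which lipids or CRP return to baseline. The overdose section's minimum monitoring time concerns drug detection and cannot stand in for it.
- **That the SAP omits outputs for these tests.** The Appendix A table titles name only hematology and chemistry, but SAP 8.3.2 promises summaries of the Table 11 parameters, and Appendix A calls its lists guidelines.

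**Conclusion.** The point holds for the visible schedule. The lipid panel and CRP have 0 of 5 scheduled on-treatment samples, against 5 of 5 for hematology and chemistry. Their scheduled data contrast pre-drug with off-drug values, so a reversible on-treatment change could be missed at every dose level. How much would be missed cannot be stated.

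The follow-up value partly helps: it can enter by-visit summaries, but it enters a worst-postbaseline shift table only if drawn within 30 days of stopping treatment, which the visit window permits without ensuring.

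This limits one part of the laboratory safety summary. It does not undermine the escalation rule or the sample size. The conclusion assumes that the extracted Table 3 is aligned, which the check rows support, and that no lipid or CRP sampling sits in the parts of the plan that are not visible.

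**What to change.** First check the full Table 3, Table 11 and Sections 8.4 and 8.5. If lipids and CRP are already drawn on treatment, make Table 3 and 8.3.5.1 show it. If not:

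- **Protocol Table 3:** add the lipid panel and CRP at Week 8, and preferably also at Week 4. Both visits already have an overnight fast and a predose safety blood draw. Keep the Safety Follow-Up sample as a recovery value.
- **SAP 8.3.2:** add wording such as: *For the lipid panel and CRP, actual values and change from Day 1 to each on-treatment visit will be summarized by treatment group; Safety Follow-Up values will be reported separately as recovery values.*
- **SAP Appendix A:** matching table titles are optional.

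The cost is a schedule amendment and about 36 extra assays of each test for Week 8 alone, or 72 of each with Week 4. No visit or fast is added. Whether another blood tube is needed cannot be seen. If the sponsor prefers the present schedule, the protocol should say why off-drug values are enough for these two tests.
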